Only data up to the Month 6 Visit of each subject will be analyzed in the interim analysis. Therefore, the cut-off date is defined as the maximum Month 6 Visit date (i.e. date of the last assessment for the Month 6 Visit). For subjects with a missing Month 6 Visit the cut-off date will be 180 days after start of study medication. This includes subjects who discontinued before Day 180.

- Cut-off date (Month 6 Visit done) = Maximum Month 6 Visit date
- Cut-off date (Month 6 Visit not done) = Start of study medication + 180 days

All events of death will be included in the interim analysis regardless of the timepoint (i.e. any death that is included in the database at the time of the snapshot will be reported in the interim analysis).

All data included in the IA will undergo a data cleaning process, however, as the key data point is an ePRO and no decisions on further study conduct are based on this IA, it is not required to have all data 100% cleaned. The quality of the data will be reviewed during the Data Review Meeting.

Data handling after cut-off date

Data after cut-off do not undergo the cleaning process.

Data other than the date of death obtained after the cut-off will not be displayed in any listings or used for summary statistics.

If the stop date for an AEs is after the date of cut-off, the AEs will be considered as ongoing during the Interim Analysis.

6.1.2 1-year Interim Analysis

A second unplanned IA will be undertaken after all subjects have completed the initial 12-month assessment.

The interim analysis will focus on the new defined tertiary endpoint, the change in Multiple Sclerosis Quality of Life-54 (MSQoL 54) physical and mental health composite scores at the Month 12 Visit compared to Baseline, which will be analyzed applying the same methodology as specified for the primary endpoint the MSQoL 54 at Month 24 (see section 14.1 for details) except for the repeated visit effect as there is only one post-baseline assessment in this analysis. As a sensitivity analysis, the analysis will be repeated by the subgroup “Previous treatment with DMDs” (Section 8.2). In order to evaluate a potential impact of the Coronavirus disease 2019 (COVID-19) pandemic on the QoL of patients, the analysis will also be repeated by a subgroup of patients that had their Month 12 MSQoL assessment after the start of the COVID-19 pandemic versus patients that had their results already reported before this date.

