Analysis (Analysis Set)	Derivation	Statistical Analysis Methods	Missing data handling
CCI			

As this IA is unplanned, no alpha spending was planned to control for overall type-I-error inflation and no stopping rules or any other modifications to the study are defined with this IA.

In addition, the Interim Analysis will describe the following characteristics of the study population:

- Disposition (Section 10.1) including and up to the cut-off point,
- Summary of visits / MSQoL assessments performed before and after start of COVID-19 pandemic,
- Baseline Characteristics including MS Disease Characteristics and results from the central MRI review for the screening MRI (Section 11),
- Relevant Previous Medication (Section 12),

and will include the following endpoints:

- Change in MSQoL Overall quality of life at the Month 12 Visit compared to Baseline (Section 14.3.1)
- Global satisfaction, Treatment effectiveness, Side effects, and Convenience assessed by TSQM v1.4 at the Month 6 and Month 12 Visit (Section 14.3.2),
- Changes in level of disability as measured by EDSS, at the Month 6 and Month 12 Visit compared to Baseline (Section 14.3),
- Relapse reports including and up to the cut-off point (number and percentage of subjects with (qualifying) relapses),
- Occurrences of TEAEs and SAEs as well as Lymphocyte counts including and up to the cut-off point (Section 15).

These characteristics will be summarized descriptively up to Month 12a Visit in the same way as for the final analysis. In addition, all TSQM scores will be analyzed applying the repeated mixed-effects linear regression as specified in Section 14.3.2 (apart from the inclusion of the Visit effect for Month 24). MSQoL and selected disposition and Baseline analyses will be repeated by subgroup “Month 12 MSQoL assessment after start of COVID-19 pandemic”.

Table 2 lists all assessments which will be included in the 1-year interim analysis.

Table 2: List of assessments included in the 1-year interim analysis

Assessments	Screening	Baseline	Month 2	Month 6	Month 12a
Informed Consent	X				
Demographic	X				
iRT		X			
Disease History	X				
CCI					
MSQoL-54		X			X
MRI	X				
CCI					
Lymphocyte Count	X	X	X	X	X
Treatment Satisfaction (TSQM v1.4)				X	X

Assessments	Screening	Baseline	Month 2	Month 6	Month 12a
Treatment Administration		X			
AEs		X	X	X	X
Treatment and Study Termination		X	X	X	X
Relevant Previous Medication	X	X			

Cut-off date

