Only data up to and including the Month 12a Visit of each subject will be analyzed in the IA. Therefore, the cut-off date is defined as the maximum Month 12a Visit date (i.e. date of the last assessment for the Month 12a Visit). For subjects with a missing Month 12a Visit the cut-off date will be 360 days after start of study medication. This includes subjects who discontinued before Day 360.

- Cut-off date (Month 12a Visit done) = Month 12a Visit End Date (i.e. Maximum Month 12a Visit date)
- Cut-off date (Month 12a Visit not done) = Start of study medication + 360 days -1

Any assessments from the Month12b or later Visits will not be included in the IA, however, any events or concomitant medications reported during these visits that have an onset/start date before or at the cut-off date will be included.

All events of death will be included in the interim analysis regardless of the timepoint (i.e. any death that is included in the database at the time of the snapshot will be reported in the interim analysis).

All data included in the IA will undergo a data cleaning process, however, as the key data point is an ePRO and no decisions on further study conduct are based on this IA, it is not required to have all data 100% cleaned. The quality of the data will be reviewed during the Data Review Meeting.

Data handling after cut-off date

Data not included in the 12 month IA do not undergo the cleaning process.

Data other than the date of death obtained after the cut-off will not be displayed in any listings or used for summary statistics.

If the stop date for an AEs is after the date of cut-off, the AEs will be considered as ongoing during the Interim Analysis.

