8.2 Definition of Analysis Sets and Subgroups

Enrolled Set (ES)

All subjects enrolled in the study, i.e. all subjects with a signed informed consent.

Intent-to-treat Set (ITT)

All subjects classified as eligible (i.e. medication assigned by iRT at the Baseline Visit).

Full Analysis Set (FAS)

All subjects from the ITT treated with at least one dose of study medication.

Treatment Completer Set – Year 1 (TCS-1)

All subjects from the FAS who completed the full Treatment Course of the first year (Treatment Course 1). Subjects will be classified as Treatment Completer for the first year, if they have a compliance greater than or equal to 100% for Treatment Course 1.

Treatment Completer Set – Year 2 (TCS-2)

All subjects from the FAS who completed the full Treatment Course of the first and the second year. Subjects will be classified as Treatment Completer for the second year, if they have a compliance greater than or equal to 100% for Treatment Course 1 and Treatment Course 2 and received the treatment without delay (see Section 9 for definition).

Safety Analysis Set (SAF)

All subjects treated with at least one dose of study medication.

Unless otherwise specified, all efficacy analyses will be performed on the FAS. The primary analysis will be repeated on the Treatment Completer Sets and on the ITT, if different, to evaluate

the sensitivity of the primary results to deviations of the planned treatment regimen. Further details are given in the respective sections. All safety analyses will be performed on the SAF.

Additional Subgroup Analysis Sets

Subgroup analyses will be performed on subgroups as defined below.

Previous treatment with Disease Modifying Drugs (DMDs):

- **DMD pre-treated:** Subjects will be categorized as DMD pre-treated if they have taken DMDs any time before start of study medication. Details of the definition of DMDs are specified in Appendix 1 (Section 18.1).
- **Pre-treatment naïve:** all subjects not classified as DMD pre-treated.

Unless otherwise indicated, all descriptive statistical analyses will be presented separately for pre-treatment naïve and DMD pre-treated subjects.

Month 12 MSQoL assessment after start of COVID-19 pandemic:

- **Yes:** Date of Month 12 MSQoL assessment (if missing, Month 12a Visit End Date) after start of COVID-19 pandemic (see Section 9 for definition).
- **No:** Otherwise.

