This subgroup is used in 1-year IA and any ePRO analyses dedicated to 1-year data as specified in the respective sections.

Specific analyses as specified in the respective sections will be repeated for these subgroups.

9 General Specifications for Data Analyses

Treatment groups

The treatment group will be labeled as Mavenclad®.

Significance level

All statistical tests mentioned in this IAP are to be regarded as exploratory. All statistical tests will be performed 2-sided. If confidence intervals are to be calculated, these will be 2-sided with a confidence probability of 95%, unless otherwise specified in this IAP.

Presentation of continuous and qualitative variables

Continuous variables will be summarized using descriptive statistics, i.e. number of subjects, number of subjects with missing and non-missing values, mean, standard deviation, median, 25th Percentile - 75th Percentile (Q1-Q3), minimum, and maximum.

Qualitative variables will be summarized by counts and percentages.

Unless otherwise stated, the calculation of proportions will be based on the number of subjects of the analysis set of interest. Therefore, counts of missing observations will be included in the denominator and presented as a separate category.

In case the analysis refers only to certain Visits percentages will be based on the number of subjects still present in the study at that Visit, unless otherwise specified.

Definition of Baseline

The last non-missing measurement prior to start of study medication will serve as the Baseline measurement. Measurements performed on the day of first intake of study medication are assumed to be “prior to start of study medication” as long as it has not been confirmed that the procedure was performed afterwards. This assumption is justified as following the sequence of procedures as specified in the study protocol. The intake of study medication should be the last procedure on the visit day.

Definition of change from Baseline

Change from Baseline = Visit value – Baseline value

Percent Change from Baseline = $100 * (Visit value - Baseline value) / Baseline value$

Definition of visit dates

The visit start date is the date of the first assessment which belongs to the corresponding visit.

The visit end date is the date of the last assessment which belongs to the corresponding visit.

Definition of duration

Duration will be calculated by the difference of start and stop date + 1 in days (if not otherwise specified).

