The start of COVID-19 pandemic will be defined by country as the earliest date of either the date of the first death from COVID-19 occurred in each country according to the published data by European Centre for Disease Prevention and Control on 26th June 2020 (<https://www.ecdc.europa.eu/en/publications-data/download-todays-data-geographic-distribution-covid-19-cases-worldwide>) or 11th March 2020 (when the WHO declared COVID-19 pandemic).

Visit timing with respect to COVID-19 pandemic

A visit is defined to be performed after the start of COVID-19 pandemic if the visit end date is greater than the start of COVID-19 pandemic date.

Conversion factors

The following conversion factors will be used to convert days into months or years for all observations except Visit related dates:

- 1 month = 30.4375 days,
- 1 year = 365.25 days.

Time window

- Day 1 is the day of start of study medication, the day before is Day -1 (no Day 0 is defined).
- Study day / Treatment day is defined relative to Day 1.

The visit schedule is defined as follows:

- 1 month = 30 days,
- 1 year = 360 days,

relative to the start date of the Baseline Visit for Treatment Course 1 and relative to the start date of the Month 12b Visit as defined in the eCRF (see also Section 15.3) for Treatment Course 2.

In each analysis, should assessment be delayed, subjects' assessment data will be treated as though it occurred at the time point specified (i.e. out of visit windows will be not excluded or adjusted for any analyses) and inferences will be conducted accordingly. Thus, further time windows will not be specified.

All observations from unscheduled Visits will be included only in the analyses of Visit independent summaries (e.g. counts of events, progressions or worst value during Treatment Period) unless for the last assessment available. In this case the missing ET visit will be imputed by the unscheduled visit.

If not specified otherwise, the assessments of the ET visit will be mapped to the nearest next planned post-baseline visit with a missing assessment before or after the ET visit of the individual assessment for all statistical analyses and descriptive summaries. As not all assessments of the ET

are performed at each visit, the different assessments of the ET can be assigned to different visits. If the duration (in days) between the ET visits and two missing planned visits are equal, then the assessment will be assigned to the later visit.

Handling of missing data

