10.1 Disposition of Participants and Discontinuations

Subject disposition will be presented for the ES:

- Total number of subjects enrolled (i.e. subjects who gave informed consent),
- Number of subjects who discontinued from the study prior to treatment overall and grouped by the main reason (i.e. the Reason why the subject did not continue beyond screening as recorded in the CRF. If the Subject did not meet all Eligibility Criteria the failed specific inclusion or exclusion criteria will be provided in addition). Subjects not classified as screened failure but without treatment assignment by the iRT will be listed as “no treatment assigned”,
- Number of eligible subjects (i.e. subjects with treatment assignment by the iRT system),
 - overall and by Treatment Course, who received at least one dose of study medication,
 - who discontinued the study medication, grouped by main reason (reason from last treatment stopped),
 - who discontinued/completed the study (according to the information on the Study Termination CRF page).
- Number of visits performed before and after Start of COVID-19 pandemic
- MSQoL-54 completion status, including reasons for missing data

Percentages will be presented with respect to the number of eligible subjects.

The number of subjects in each analysis set will be provided overall, by region, by country within region and by site.

The following subject data listings will be provided:

- Listing of discontinued subjects for the ITT,
- Listing of subjects excluded from the Analysis Sets.

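### The SAP's COVID-19 subgroup puts every subject with no Month 12 assessment date in *No*, which conflicts with its own description of the comparator and distorts the subgroup counts and tables

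*SAP*

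**What the plan says.** **Definition (SAP 8.2).** *Yes* is defined as "Date of Month 12 MSQoL assessment (if missing, Month 12a Visit End Date) after start of COVID-19 pandemic (see Section 9 for definition"). *No* is simply the remainder. No third date is given for a subject who has neither of the two.

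**Visit date (SAP Section 9).** "The visit end date is the date of the last assessment which belongs to the corresponding visit". A visit that was not done has no assessments, so it has no end date.

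**Pandemic start (SAP Section 9).** This is set by country as the earlier of the first COVID-19 death there "or 11th March 2020 (when the WHO declared COVID-19 pandemic"). The latest possible start is therefore 11 March 2020.

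**Purpose (SAP 6.1.2).** The split is meant to evaluate a possible effect of the pandemic on quality of life. It compares subjects assessed at Month 12 after pandemic start "versus patients that had their results already reported before this date".

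**Use.** "This subgroup is used in 1-year IA and any ePRO analyses dedicated to 1-year data" (SAP 8.2). In the 1-year interim analysis, "MSQoL and selected disposition and Baseline analyses will be repeated by subgroup" (SAP 6.1.2). The disposition output in SAP 10.1 includes "MSQoL-54 completion status, including reasons for missing data".

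**A reference date for missed visits already exists.** For the interim data cut-off, SAP 6.1.2 states: "For subjects with a missing Month 12a Visit the cut-off date will be 360 days after start of study medication". The formula below that sentence subtracts one further day. SAP 8.2 does not use this date.

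**The concern.** The two descriptions of the comparator disagree. SAP 6.1.2 describes subjects with a result before pandemic start. SAP 8.2 takes in those subjects and also anyone with no Month 12 date at all.

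A subject due for Month 12 in spring 2020 who missed the visit would be counted with those assessed before the pandemic. Membership of *Yes* requires attendance, while *No* is part calendar period and part non-attendance.

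Missed visits are one of the things a pandemic summary should help to locate in time. Under this rule they can appear on one side only. The Baseline description of *No* also mixes subjects assessed before the pandemic with non-attenders from either period, so the two columns do not compare like with like.

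**Working it through.** The documents give no figure for this subgroup, so there is nothing to reproduce. The check is of the rule itself, followed by an illustration under stated assumptions.

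**1. The rule on each combination of dates**

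| Month 12 MSQoL-54 date | Month 12a Visit End Date | Subgroup |
|---|---|---|
| after pandemic start | any | *Yes* |
| on or before pandemic start | any | *No* |
| missing | after pandemic start | *Yes* |
| missing | on or before pandemic start | *No* |
| missing | missing | *No*, always |

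The third row shows that *Yes* can contain a missing MSQoL-54, provided some other Month 12a assessment took place. The last row shows that it can never contain a wholly missed visit.

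**2. A worked date.** Take a first dose on 1 May 2019 and no Month 12 visit. The SAP's cut-off formula gives 1 May 2019 + 360 − 1 days = 24 April 2020, which is after 11 March 2020. The rule still returns *No*. Counting back, 11 March 2020 − 359 days = 18 March 2019. For any subject first dosed after that date who has neither Month 12 date, the reference date lies after pandemic start and the label is *No*.

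**3. Illustration of size.** N = 445 is the planned number (protocol synopsis). Assumed: 55% due before pandemic start, and the same proportion m of visits wholly missed in both periods. Then:

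- Due before: 445 × 0.55 = 244.75. Due after: 445 × 0.45 = 200.25.
- *Yes* = 200.25 × (1 − m), all of whom attended.
- *No* = 244.75 + 200.25 × m, of whom 244.75 × (1 − m) attended.

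| m | True attendance, both periods | *Yes*: n, attended | *No*: n | *No*: attended |
|---|---|---|---|---|
| 5% | 95% | 190.2, 100% | 254.8 | 232.5 (91%) |
| 10% | 90% | 180.2, 100% | 264.8 | 220.3 (83%) |
| 15% | 85% | 170.2, 100% | 274.8 | 208.0 (76%) |

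The true difference between periods is zero in every row. The table would show 9, 17 and 24 points.

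**4. Other assumptions.** Take 5% missed before pandemic start, 5% to 20% missed after it, and 30%, 50% or 70% of visits due after it. The share of wholly missed visits in *No* then runs from 7.0% (30% due after, 5% missed) to 35.2% (70% due after, 20% missed). In *Yes* it is always 0%. With 50% due after and 10% of those missed, the rates by due date are 5% before and 10% after, but the subgroup table shows 13.6% in *No* and 0% in *Yes*, so the direction is reversed.

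**5. Which outputs are touched.** The 1-year model has a single post-baseline visit, and missing post-baseline values are not imputed (SAP 6.1.2, 14.1.1). A subject with no Month 12 score adds no outcome to either subgroup. Subgroup N, missing counts and the tables by subgroup are affected. SAP Section 14 takes observed margins from the whole analysis set, including subjects with missing data. If this is applied per subgroup, non-attenders also shift the *No* LS means. SAP 14.1.1 names the FAS for the primary model, so this last effect is conditional.

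**The case against.** The strongest reply is that the consequences are limited, and much of it stands.

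- **The estimates.** A reader might infer that the Month 12 quality-of-life comparison is itself biased by the misplaced subjects. The documents do not support that: subjects without a score contribute no change score.
- **MSQoL-54 completeness.** A reader might infer that questionnaire completion in the pandemic period would look perfect. It need not, because a subject who attended Month 12a without completing the questionnaire is in *Yes*. The 100% above is visit attendance. SAP 6.1.2 repeats only selected disposition analyses by subgroup and does not say that completion status is among them.
- **Other COVID-19 outputs.** The subgroup is not the SAP's only view of the pandemic. It also plans counts of visits and MSQoL assessments before and after pandemic start (6.1.2, 10.1), reasons for missing MSQoL-54 (10.1), major deviations by relationship to COVID-19 (10.2.1) and start of Course 2 before or after pandemic start (Section 13). The counts cover visits performed, so they cannot show those missed. The deviations and reasons may show the cause, but they do not correct the split.
- **Number affected.** Early Termination assessments are mapped to missing planned visits, so some discontinuers will have a Month 12 date. A postponed visit held after pandemic start is correctly *Yes*. Visit-specific percentages use subjects still in the study.
- **The label.** It says *No*, not pre-pandemic, and for a subject never assessed that is literally true. The pre-pandemic reading comes from SAP 6.1.2, which is why the two sections must be reconciled.

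The analysis is also exploratory, and no decisions on study conduct rest on the 1-year interim.

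**Conclusion.** The point holds as a defect in the subgroup definition. As written, *No* combines subjects assessed on or before pandemic start with all subjects who have no Month 12 date, contrary to SAP 6.1.2. The direction is fixed by the rule: wholly missed visits can appear only in *No*.

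The damage is to subgroup sizes, missing counts and the Baseline and selected disposition tables by subgroup, and to LS means only if margins are taken per subgroup. The observed Month 12 change scores stand.

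The size is not known. It depends on how many subjects have neither an MSQoL-54 date (including a mapped Early Termination assessment) nor a Month 12a visit, which the documents do not state. The 91% to 76% range rests on the assumed 55% split and 5% to 15% missed rates, and takes all 445 planned subjects as still due for the visit. It shows what the rule can do and is not an estimate for this trial. The correction is worth making because it is cheap and the stated rule does not produce the stated comparison.

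**What to change.** In SAP 8.2:

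1. Restrict *No* to subjects whose Month 12 MSQoL-54 date, or Month 12a Visit End Date if that is missing, is on or before the country's pandemic start. This matches the timing described in SAP 6.1.2.
2. Put subjects with neither date in a separate category, *no Month 12 assessment*. This keeps the *Yes* label true, which moving them into *Yes* would not.
3. Within that category, split subjects still in the study by whether their due date falls before or after pandemic start. Two dates are available: Baseline Visit start + 360 days, which follows the visit schedule in SAP Section 9, or start of study medication + 360 − 1 days, which SAP 6.1.2 uses as a data cut-off rather than a scheduled date. Name one.
4. Show subjects who discontinued before that date on their own row.
5. State whether observed margins for the subgroup models come from the FAS or from each subgroup.

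The cost is a few sentences in the SAP and a small change to one derivation, using data already held. The downside is an extra category or row in the subgroup tables.
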